## 15.5 Safety Analysis

Safety variables to be analyzed by dose level and tumor type are AEs, laboratory test results (hematology, coagulation, serum chemistry, and urinalysis), ECG, weight, and vital signs. Adverse event terms recorded on the eCRFs will be mapped to preferred terms using the most recent version of the Medical Dictionary for Drug Regulatory Activities (MedDRA®). All AEs will be summarized according to the system organ class and preferred term within the organ class. Adverse events will be tallied for overall frequency (number and percentage of patients), worst reported severity, and relationship to study treatment for each preferred term per patient. Serious adverse events will be similarly summarized. Listings of deaths, SAEs, and AEs leading to early termination of study treatment or premature withdrawal from study will also be provided.

Laboratory variables will be examined using mean change in value from baseline to scheduled time points. The baseline value of a variable is defined as the last value obtained on or before the date and time of the first dose of INCB001158 or pembrolizumab.

ECG, weight, and vital signs will also be summarized by changes from baseline to scheduled time points using descriptive statistics.

## 15.6 Pharmacokinetic Analysis

For Part 1a- Dose Escalation PK samples, a noncompartmental method of analysis will be used to analyze the plasma concentrations of INCB001158. The maximum plasma concentration ( $C_{max}$ ) and the time to attain the  $C_{max}$  ( $T_{max}$ ) will be determined directly from the observed data. In Part 1a, full AUC ( $AUC_{0-12\text{ hr}}$ ) will be calculated on Days 1 and 15 in Cycle 1.

For Parts 1b, 2a, 2b, 2c, and 3, sparse sampling will be collected to confirm exposure and to explore population PK (see [Attachment 1A](#) and [1B](#)).

For Part 1c, a noncompartmental method of analysis will be used to analyze the plasma concentrations of INCB001158. The log-transformed PK parameters will be compared between renally impaired patients (CrCl 30-49 mL/min) and patients with normal renal function (CrCl  $\geq$  50 mL/min) using an analysis of variance. The geometric mean relative bioavailability and 90% confidence intervals for INCB01158  $C_{max}$  and AUC will be calculated using the inpatient variability from the ANOVA model to assess the magnitude of the difference between the patients with normal renal function and those with moderate renal impairment.

[REDACTED]

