#### **Statistical Methods**

##### **Sample Size Method**

The primary objective is to determine a dose level of INCB001158, as monotherapy and in combination with pembrolizumab, for which the rate of DLTs is less than 33%. Up to approximately 108 patients are planned for single agent dose escalation (Part 1a) and up to 108 patients for combination dose escalation (Part 1b).

Part 1c is intended to enroll the minimum number of patients required to generate sufficient PK data for a descriptive comparison of Day 1 and steady state (Day 8, Day 15) exposures between patients with moderate renal impairment (CrCl 30-49 mL/min) and normal renal function (CrCl > 50 mL/min). Accordingly, the sample size of 6 PK-evaluable patients for Cohort 1c is not based on a predefined statistical analysis.

In Parts 2a, 2b, and 3, the sample size for each tumor type within a treatment group will be guided by the Simon 2-stage design. Part 2c is designed to investigate the potential for clinical activity in a variety of tumor types. The sample size for the initial 30 patients was not based on a predefined statistical analysis. The sample size for each tumor type in any subsequent expansion of Cohort 2c will be guided by a Simon 2-stage design.

Each Simon 2 stage design will have a stopping rule to allow early termination of a particular tumor type within a treatment group at the end of Stage 1 if there is insufficient response observed, while enrolling enough patients to predict possible target responses worthy of cohort expansion and potentially further evaluation in future studies.

The proposed designs for each tumor type will be used for any planned Simon 2-stage design. Each Simon 2-stage design is set up to have a 1-sided Type I error of 0.1 and power of 80%. The response rates for each tumor type will be estimated with 95% confidence intervals.

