- At least half of the patients (minimum of 2 patients) achieve the target exposure leading to continuous inhibition of extracellular arginase 1 by > 90% (a trough [Cmin] plasma concentration of INCB001158 at steady state of  $\geq 1$   $\mu$ M), AND/OR
- At least half of the patients (minimum of 2 patients) achieve a 2.5-fold increase in fasting plasma arginine at Cycle 1 Day 15 predose relative to their baseline (Cycle 1 Day 1 predose) value.

Population PK modeling showed a highly predictable, linear, inverse relationship between CrCl and AUC, Cmax, and half-life for INCB001158 (see Section 10.2.2.1). Therefore, if the PK-PD criteria specified above are not met at the 50 mg BID dose, population PK modeling will be used to determine whether a lower dose (25 mg BID) or a previously evaluated intermediate dose (75 mg BID) would more closely approximate PK parameters for the established RP2D of 100 mg BID. Cohort 1c patients who do not complete all planned PK assessments or have treatment discontinuation or interruptions during the first 21 days of dosing will be replaced until 6 evaluable patients have been accrued to the cohort. Patients meeting the pre-specified PK and PD criteria will be counted towards the Simon 2-stage efficacy assessment in their respective Part 3 expansion cohorts, provided these have not fully enrolled at the time data from these patients become available.

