The overall safety profile across 3 INCB001158 dose levels evaluated in combination with pembrolizumab was favorable, with no DLTs or Grade 3 treatment-related AEs at the maximum

dose level of INCB001158 100 mg BID. INCB001158 PK and PD in combination with pembrolizumab were similar to that of INCB001158 monotherapy, with similar exposures at equivalent doses and strong target inhibition, as indicated by increases in plasma arginine. The RP2D for INCB001158 alone and in combination with pembrolizumab was declared as 100 mg BID. Therefore, evaluation of INCB001158 in patients with moderate renal impairment will be done in combination with pembrolizumab, since pembrolizumab did not have any effect on INCB001158 exposure.

In order to determine the appropriate dose in patients with moderate renal impairment (defined as CrCl 30-49 mL/min), population PK modeling was performed, incorporating full PK data from patients enrolled to the already completed dose escalation parts in patients with CrCl  $\geq$  50 mL/min. The PK data showed that INCB001158 AUC,  $C_{max}$ , and half-life inversely correlated with CrCl across all tested doses, as expected (Figure 10.2-1). Based on the strongly inverse linear relationship between CrCl and AUC, extrapolation of the data to CrCl values below 50 mL/min indicated that a dose of 50 mg BID in patients with CrCl 30 to 49 mL/min predicted INCB001158 AUC values to fall within the known safe exposure range corresponding to doses at or below the established RP2D of 100 mg BID (Table 10.2-1).

[figure not shown]

Figure 10.2-1: Plot of INCB001158 CrCl versus AUC or  $C_{max}$  in patients treated with INCB001158 alone or in combination with pembrolizumab, from Parts 1a and 1b.

**Table 10.2-1: Projected Human INCB001158 Steady-State AUCs During 1 Dose Interval at 50, 75, 100, and 150 mg for Patients with Different Creatinine Clearances Ranging from 15 to 200 mL/min**

CrCl (mL/min)	AUC (50 mg)	AUC (75 mg)	AUC (100 mg)	AUC (150 mg)
15	41,210	61,815	82,420	123,630
20	31,283	46,924	62,565	93,848
30	21,355	32,033	42,710	64,065
40	16,391	24,587	32,783	49,174
50	13,413	20,120	26,826	40,239
60	11,428	17,141	22,855	34,283
70	10,009	15,014	20,019	30,028
80	8,946	13,418	17,891	26,837
90	8,118	12,178	16,237	24,355
100	7,457	11,185	14,913	22,370
110	6,915	10,373	13,830	20,745
120	6,464	9,696	12,928	19,391
130	6,082	9,123	12,164	18,246
140	5,755	8,632	11,509	17,264
150	5,471	8,207	10,942	16,413
200	4,478	6,717	8,957	13,435

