**Table 15.2-1: Summary of Sample Size and Power for Expansion Cohorts**

Cohort	p0 Background ORR (%)	p1 Target ORR (%)	$\alpha$	Power (%)	n1 for Stage 1 (r1)	n2 (n - n1) for Stage 2	Total n (r2)
2a	2%	15%	0.1	80	11 (0)	15	26 (1)
2b	2%	15%	0.1	80	11 (0)	15	26 (1)
2c expansion	2%	15%	0.1	80	11 (0)	15	26 (1)
3a	2%	15%	0.1	80	11 (0)	15	26 (1)
3b	2%	15%	0.1	80	11 (0)	15	26 (1)
3c	2%	15%	0.1	80	11 (0)	15	26 (1)
3d	2%	15%	0.1	80	11 (0)	15	26 (1)
3e	2%	15%	0.1	80	11 (0)	15	26 (1)
3f	10%	25%	0.1	80	13 (1)	21	34 (5)
3g	20%	40%	0.1	80	12 (2)	13	25 (7)
3h	13%	30%	0.1	80	10 (1)	23	33 (6)

Cohort 2c is designed to generate additional evidence of clinical activity in a variety of tumor types. The sample size for the initial 30 patients was not based on a predefined statistical analysis. The sample size for each tumor type in any subsequent expansion of Cohort 2c will be guided by a Simon 2-stage design.

Part 1c is intended to enroll the minimum number of patients required to generate sufficient PK data for a descriptive comparison of Day 1 and steady state (Day 8, Day 15) exposures between patients with moderate renal impairment (CrCl 30-49 mL/min) and normal renal function (CrCl

> 50 mL/min). Accordingly, the sample size of 6 PK-evaluable patients for Cohort 1c is not based on a predefined statistical analysis.

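### The Part 1c renal comparison in Protocol 15.6 ignores CrCl within its reference group, so the reported exposure ratio depends on the reference patients' CrCl mix; a continuous-CrCl analysis should be added

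*Protocol*

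**What the plan says.** Protocol Section 15.6 plans noncompartmental analysis for Part 1c and then an analysis of variance: "The log-transformed PK parameters will be compared between renally impaired patients (CrCl 30-49 mL/min) and patients with normal renal function". There the second group is defined as CrCl of at least 50 mL/min. The output is described as "The geometric mean relative bioavailability and 90% confidence intervals for INCB01158" Cmax and AUC. The visible text names no CrCl covariate, upper limit, banding or matching. It does not say which study parts or doses supply the reference patients, or whether values are dose-normalised.

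The Synopsis (Sample Size Method) and Section 15.2 call the comparison descriptive but draw the boundary differently, as "normal renal function (CrCl > 50 mL/min". They add that "the sample size of 6 PK-evaluable patients for Cohort 1c is not based on a predefined statistical analysis".

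Elsewhere the protocol treats CrCl as a strong predictor of exposure. In Section 5.1 (Part 1c): "Population PK modeling showed a highly predictable, linear, inverse relationship between CrCl and AUC", together with Cmax and half-life. Section 10.2.2.1, drawing on dose-escalation patients with CrCl of at least 50, reports that AUC, Cmax and "half-life inversely correlated with CrCl across all tested doses". Table 10.2-1 in that section projects steady-state AUC by dose for CrCl from 15 to 200 mL/min.

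**The concern.** Part 1c is meant to identify the exposure in moderate renal impairment that best matches 100 mg BID in patients with normal renal function. A group defined only by a lower limit of 50 mL/min is not one exposure level. On the protocol's own projection it runs from values close to those of the impaired group down to about a third of its own maximum.

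A two-group comparison treats that predictable variation as residual noise, and its reference mean is set by whichever CrCl values happen to be present. The same drug behaviour could then be reported as lower, equal or higher exposure in the impaired group. The reader could not tell how much of the ratio reflects renal impairment and how much reflects the composition of the comparator. The reference could also be small: Section 11.9.2 gives intensive sampling only to Parts 1a and 1c, and Figure 10.1-7 describes 4 patients at 100 mg in early data.

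**Working it through.** **Inputs (Table 10.2-1).** AUC at 50 mg, CrCl 40: 16,391. AUC at 100 mg: 32,783 (CrCl 40), 26,826 (50), 22,855 (60), 16,237 (90), 12,928 (120), 8,957 (200).

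**Step 1: reproduce the table.** The formula AUC = (dose/50) × (1,500 + 595,651/CrCl) returns every row of the 50 mg column within 0.5 unit. The other columns are dose multiples within 1 unit. The projection is therefore a smooth function of CrCl with exact dose proportionality built in.

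**Step 2: spread inside the reference group at 100 mg.**
- CrCl 50 against 120: 26,826 / 12,928 = 2.08.
- CrCl 50 against 200: 26,826 / 8,957 = 2.99.
- For comparison, CrCl 40 against 50: 32,783 / 26,826 = 1.22, and CrCl 50 against 90: 26,826 / 16,237 = 1.65. A reference patient at CrCl 50 is projected to be nearer to an impaired patient at 40 than to another reference patient at 90.

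**Step 3: effect on the ratio of 50 mg at CrCl 40 to 100 mg in the reference.**
- Reference at CrCl 60: 16,391 / 22,855 = 0.72.
- Reference at CrCl 90: 16,391 / 16,237 = 1.01.
- Reference at CrCl 120: 16,391 / 12,928 = 1.27.

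**Step 4: mixtures instead of single values.** Assume impaired CrCl is uniform on 30-49, which gives a geometric mean AUC of 16,742 at 50 mg. The expected ratio to 100 mg is then 0.68, 0.82, 0.96, 1.07 and 1.25 for reference CrCl uniform on 50-60, 50-90, 50-120, 50-150 and 50-200. These mixes are assumptions; the actual distribution is not given.

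**Step 5: simulation under the table's relation.** Assumptions: 6 Part 1c patients with CrCl 30-49, 12 reference patients at 100 mg, residual SD of log AUC 0.15 or 0.25. The two-group ratio averages about 0.82, 1.00 and 1.23 for reference CrCl 50-90, 50-130 and 80-150. A regression of log dose-normalised AUC on log CrCl, read at 40 against 90, averages 0.99 to 1.02 in all three.

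**Step 6: what if Part 1c patients depart from the relation?** Give them a true 1.3-fold excess. The two-group ratio then averages from 1.07 (reference 50-90) to 1.61 (80-150). The regression read at 40 against 90 averages 1.36, 1.22 and 1.19 for mixes 50-90, 50-130 and 80-150. It is less mix-dependent, but biased.

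**Step 7: precision.** With reference CrCl 50-130 and 12 reference patients, the ratio of upper to lower 90% limit falls from 1.54 to 1.26 (SD 0.15) or from 1.74 to 1.46 (SD 0.25). With reference CrCl 50-90 there is no reliable gain, and at SD 0.25 the interval is slightly wider.

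**Step 8: dose proportionality in observed data.** Table 10.1-1 gives mean AUC of 30.2, 80.6 and 85.5 µM·hr at 50, 100 and 150 mg. Per 100 mg that is 60.4, 80.6 and 57.0, a spread of 80.6 / 57.0 = 1.41. Differing CrCl between small cohorts might explain this, but the documents do not show it.

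**The case against.** The strongest reply is that the ANOVA does not decide the dose. The Synopsis and Section 5.1 say first-cycle data are evaluated together with population PK modelling, which already relates exposure to CrCl. If the stated trough and arginine criteria are not met, that modelling is used to assess the alternatives. No visible text makes the ANOVA ratio a criterion. The comparison is called descriptive, the SAP (3.2) calls all statistical analyses exploratory, and the SAP Introduction defers PK methods to a separate document. Text after the Part 1c paragraph in 15.6 is also redacted. All of this stands and limits the consequence, but none of the visible text corrects the ratio or its interval.

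Second, average exposure in patients actually treated at 100 mg BID is a defensible comparator. A ratio near 0.82 against patients with CrCl 50-90 is correct for those patients. This also stands. A reader might take simulated frequencies with which the 90% CI excludes 1 as error rates of the ANOVA. They are not, because a true ratio of 1 follows only from choosing CrCl 90 as the reference, and the documents do not name that value as the target. Read at 60 or 120, the regression itself gives about 0.71 or 1.28.

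Third, a reader might conclude that regression should replace the ANOVA and would remove the problem at no cost. The documents do not support that. The model was built at CrCl of at least 50 and extrapolated downward, so a single slope is biased if the relation differs below 50 (Step 6), and observed dose proportionality is not clean (Step 8).

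Finally, the 3-fold figure needs a patient at CrCl 200. Over 50-120 the spread is about 2-fold.

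**Conclusion.** The point holds as a cheap improvement to the reported analysis. As visible, 15.6 yields a ratio whose value depends on an unstated CrCl mix: on the protocol's own table, from 0.72 to 1.27 as the reference CrCl moves from 60 to 120. This rests on Table 10.2-1 being approximately right within the reference group. The mixture and simulation results additionally rest on assumed CrCl distributions, sample sizes and residual SDs, and are illustrative.

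A reader might infer that the Part 1c dose decision itself is compromised. The documents do not support this, given the role of population PK modelling and the descriptive status of the comparison. What is affected is the interpretability of the ratio and its 90% CI.

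**What to change.** In Section 15.6 and the separate PK analysis plan:

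- Keep the two-group ratio and add a model of log AUC and log Cmax on continuous log CrCl.
- Report the predicted ratio with 90% CI at several stated CrCl values, for example 30, 40 and 49 mL/min, each against more than one prespecified reference value, with the choice justified.
- Show the CrCl distribution of both groups, and state which parts and doses supply the reference patients.
- Label the reference as CrCl of at least 50 mL/min rather than normal, and reconcile that limit with the strict inequality in the Synopsis and Section 15.2.
- Use reference patients treated at 100 mg, or dose-normalise with a check of proportionality.
- Check whether Part 1c patients depart from the fitted line, for example with a group term as a sensitivity analysis.

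The cost is wording and a small amount of programming; no new patients or measurements are needed. The downside is reliance on log-linearity in CrCl and, if doses are pooled, on dose proportionality. There is little or no gain in precision if reference CrCl turns out to be confined to 50-90.

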### 15.7 Precautions

Although major adverse events are not anticipated, the Investigator must proceed with utmost caution. Equipment, supplies, and properly skilled medical personnel must be immediately available for emergency use in the event of an unexpected reaction. Patients must be selected carefully and closely monitored.

For a complete description of preclinical studies of INCB001158, please refer to the INCB001158 Investigator's Brochure. For a description of precautions with pembrolizumab, please refer to the Product Label.

## 16.0 SAFETY MONITORING AND REPORTING

### 16.1 Adverse Events

#### 16.1.1 Definitions

For the purposes of this Protocol, an adverse event (AE) is defined as any untoward medical occurrence associated with the use of a drug in humans, whether or not considered drug related, that occurs after a subject provides informed consent. Abnormal laboratory values or test results occurring after informed consent constitute AEs only if they induce clinical signs or symptoms, are considered clinically meaningful, require therapy (eg, hematologic abnormality that requires transfusion), or require changes in the study treatment(s).

#### 16.1.2 Reporting

Adverse events that begin or worsen after informed consent should be recorded on the Adverse Events form of the eCRF. Conditions that were already present at the time of informed consent should be recorded on the Medical History form in the eCRF. Monitoring for the occurrence of new AEs should be continued for up to 30 days after the last dose of study treatment or until the start of new anticancer therapy, whichever occurs first. Adverse events (including laboratory abnormalities that constitute AEs) should be described using a diagnosis whenever possible rather than by individual underlying signs and symptoms. When a clear diagnosis cannot be identified, each sign or symptom should be reported as a separate AE.

The term "disease progression" should be recorded as an AE/SAE only if there are no other identifiable AEs/SAEs associated with the disease progression at the time of reporting. For events associated with disease progression, the relevant signs and symptoms should be reported using a diagnosis whenever possible rather than individual underlying signs and symptoms. When a clear diagnosis cannot be identified, each sign or symptom should be reported as a separate AE. If the events resulting from disease progression meet the criteria for an SAE (eg, resulted in hospitalization, a life-threatening event, or death), the specific event(s) should be reported as an SAE(s) as described in Section 16.3.2. In both cases (ie, AEs or SAEs related to disease progression), it should be indicated that each event (reported as a diagnosis or as signs and symptoms) is related to disease progression on the Adverse Events form of the eCRF.

The severity of AEs will be assessed using CTCAE v4.03 Grades 1 through 5. If an event is not classified by CTCAE, the severity of the AE will be graded according to the scale below to estimate the grade of severity:

Grade 1	Mild; asymptomatic or mild symptoms; clinical or diagnostic observations only; intervention not indicated.
Grade 2	Moderate; minimal, local, or noninvasive intervention indicated; limiting age-appropriate activities of daily living.
Grade 3	Severe or medically significant but not immediately life-threatening; hospitalization or prolongation of hospitalization indicated; disabling; limiting self-care activities of daily living.
Grade 4	Life-threatening consequences; urgent intervention indicated.
Grade 5	Fatal

The occurrence of AEs should be sought by nondirective questioning of the subject during the screening process after signing the ICF and at each visit during the study. Adverse events may also be detected when they are volunteered by the subject during the screening process or between visits, or through physical examination, laboratory test, or other assessments. To the extent possible, each AE should be evaluated to determine:

- The severity grade (CTCAE Grade 1 to 5).
- Whether there is at least a reasonable possibility that the AE is related to the study treatment: suspected (yes) or not suspected (no). Relatedness will be assessed for each of INCB001158 (all Parts) and pembrolizumab (Parts 1b and 3 only).
- The start and end dates, unless unresolved at final follow-up.
- The action taken with regard to study drug.
- The event outcome (eg, not recovered/not resolved, recovered/resolved, recovering/resolving, recovered/resolved with sequelae, fatal, unknown).
- The seriousness, as per serious adverse event (SAE) definition provided in Section 16.3.1.

Unlike routine safety assessments, SAEs are monitored continuously and have special reporting requirements (see Section 16.3.2).

All AEs should be treated appropriately. If an AE is treated with a concomitant medication or nondrug therapy, this action should be recorded on the Adverse Event form in the eCRF and the

treatment should be specified on the Prior and Concomitant Medications or Procedures form in the eCRF.

Once an AE is detected, it should be followed until it has resolved or until it is judged to be permanent; assessment should be made at each visit (or more frequently if necessary) of any changes in severity, the suspected relationship to the study drug, the interventions required to treat the event, and the outcome.

When the severity of an AE changes over time for a reporting period (eg, between visits), each change in severity will be reported as a separate AE until the event resolves. For example, 2 separate AEs will be reported if a subject has Grade 1 diarrhea, meeting the definition of an AE, that lasts for 3 days before worsening to a Grade 3 severity. The Grade 1 event will be reported as an AE with a start date equal to the day the event met the Grade 1 AE definition and a stop date equal to the day that the event increased in severity from Grade 1 to Grade 3. The Grade 3 event will also be reported as an AE, with the start date equal to the day the event changed in intensity from Grade 1 to Grade 3 and a stop date equal to the day that the event either changed severity again or resolved.

